1) Tetrahydrocannabinol (THC) has been the primary focus of cannabis research since its isolation and synthesis in 1964 (Gaoni and Mechoulam 1964). Currently there is a lot of debate regarding whether, and which, non-THC constituents of the cannabis plant contribute to the overall pharmacodynamic effects of cannabis. In recent publications, Ethan Russo has hypothesized that specific cannabis terpenoids, aromatic essential oil (EO) components, may selectively mitigate or exacerbate some acute effects of THC (McPartland and Russo 2001, Russo 2011, McPartland and Russo 2014). This purported “entourage effect” has been the driving force behind state legalization of cannabis for medicinal purposes despite THC (as dronabinol) being available as an FDA approved medication. However, there have been no empirical research studies conducted to evaluate the interactions of THC and terpenoids found in the cannabis plant. The proposed study will be a controlled human laboratory evaluation of the acute dose effects of THC and d-limonene (limonene) alone and in combination. Limonene is a flavor and fragrance component common to many plants, is one of the most abundant terpenoids in cannabis, is a fragrance ingredient in many household products, and is part of the typical human diet as it is present in most citrus fruits. Oral ingestion of d-limonene is Generally Recognized as Safe (GRAS) by the US Food and Drug Administration and other regulatory agencies, and studies have been conducted evaluating its effects when inhaled in ambient air. Prior research has demonstrated that limonene inhaled from ambient air can produce anxiolytic effects and reduce depression (Buchbauer et al. 1993, Carvalho-Freitas and Costa 2002a, Pultrini Ade, Galindo, and Costa 2006, Falk-Filipsson et al. 1993). This study will evaluate whether limonene, compared with placebo, attenuates increases in anxiety that often occur following acute THC administration. A controlled laboratory study will be conducted with healthy adults who have experience inhaling cannabis. Participants will complete 9 acute drug administration sessions at the Behavioral Pharmacology Research Unit (BPRU). Sessions will involve double blind administration of: 1) Placebo, 2) 15mg THC, 3) 30mg THC, 4) 1mg d-limonene, 5) 5mg d-limonene, 6) 15mg THC + 1mg d-limonene, 7) 30mg THC + 1mg d-limonene, 8) 15mg THC + 5mg d-limonene, and 9) 30mg THC + 5mg d-limonene via vaporization. Participants who complete these 9 primary conditions, and who exhibit increased anxiety after THC exposure, will be invited to complete an optional 10th study condition in which they administer 30mg THC + 15mg d-limonene to determine whether a higher dose of d-limonene can further attenuate the anxiogenic effects of THC than what is observed at the 1mg and 5mg doses. At baseline and following drug administration, a battery of subjective, physiological, and cognitive performance assessments will be completed and biological specimens obtained. The study will conclude when 20 participants complete all 9 primary experimental sessions. The outcomes of this study will be

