The primary doses of d-limonene to be used in this study (1mg and 5mg) are within the range of what would be inhaled by an individual who smokes 1 gram of cannabis. In recent research studies conducted in our laboratory, 1 gram is the amount of plant material commonly used to make a single cannabis cigarette ("joint" or "blunt"). In addition, chemical analysis of 107 samples of cannabis consisting of 29 different "strains" of cannabis produced by a Canadian medicinal cannabis manufacturer indicate that 1 mg would be the median and 5mg would be the maximum d-limonene dose in a 1 gram cannabis cigarette produced with their products. Thus, these doses are ecologically relevant and have demonstrated safety with respect to acute dosing via direct inhalation. The optional 15mg dose of d-limonene is higher than what would typically be consumed in natural botanical cannabis, but should not present any risk of harm. A current practice in the cannabis industry is to supplement formulated cannabis products with extracted terpenes. Further evidence for the safety of d-limonene comes from a prior study (Falk-Filipsson et al., 1993) in which healthy adults were continuously exposed to high levels of d-limonene in an enclosed chamber for 2 hours; in this study, participants absorbed up to about ~26 mg of d-limonene without experiencing adverse events or irritative symptoms. At the time that the amendment to this protocol adding the 15mg d-limonene dose was submitted, no adverse effects had been reported following either 1mg or 5mg d-limonene administration for the first 16 randomized participants. The results of this study will represent a significant initial advancement in understanding the behavioral pharmacology of cannabis. This is the initial study in a series of similar experiments funded by NIH in which we will begin to systematically evaluate the interactions of multiple components of the cannabis plant. Characterization of the interaction between THC and d-limonene will provide an initial scientific basis for whether or not there is benefit for including terpenoids in the development of cannabinoid-based pharmaceutical products as one means of reducing the incidence and/or severity of side effects.

4. Study Procedures

- Study design, including the sequence and timing of study procedures (distinguish research procedures from those that are part of routine care).

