Protocol Overview. The proposed study will be conducted at the Johns Hopkins Behavioral Pharmacology Research Unit (BPRU). The purpose of the study is to examine the behavioral pharmacology of THC, d-limonene, and their combination versus placebo. All procedures will be performed in double-blind manner using a within-subject crossover design. Participants will be healthy adults with a history of having experienced mild to moderate anxiety following acute cannabis exposure, but will not be daily cannabis users. A total of 9 primary outpatient drug administration sessions will be conducted for each evaluable participant. Study completers who report increased anxiety after THC exposure will be invited to complete an optional 10th study condition with a higher dose of d-limonene.

- 1) Placebo (5mL distilled water)
- 2) THC (15 mg)
- 3) THC (30 mg)
- 4) D-Limonene (1 mg)

- 5) D-Limonene (5 mg)
- 6) THC (15 mg) + D-Limonene (1 mg)
- 7) THC (30 mg) + D-Limonene (1 mg)
- 8) THC (15 mg) + D-Limonene (5 mg)
- 9) THC (30 mg) + D-Limonene (5 mg)
- 10) THC (30 mg) + D-Limonene (15 mg) – optional for select study completers only

We will obtain a battery of pharmacodynamic outcome measures at baseline and for 6 hours after each dose. Sessions will be conducted at a target rate of 1-2 times per week, with a minimum of 3 days between experimental sessions. We will recruit study volunteers until 20 participants complete the protocol. Participants who drop out of the study prior to completion of all scheduled sessions will be considered “incomplete” and will be replaced. Drug administration sessions will be completed in a randomized order because there are too many dose conditions to properly counterbalance the order across 20 study completers. The optional 10th condition will not be randomized and will only occur after the other nine study conditions have been completed and the PI has determined that the participant exhibited an anxiogenic response to THC during initial test sessions.

Participants. We will recruit and consent up to 65 research volunteers in order to obtain 20 study completers. We anticipate that about 50% of those screened will not be eligible or interested in the study, and that post-randomization some participants may drop out of the study before completion. It is estimated that we will need to randomize 32 participants to achieve 20 completers given the length of the protocol.

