A pharmacist or other qualified technician will apply test substances with a micro-pipette into a dosing capsule, accessories that come with the Mighty Medic. For each experimental session, a dosing capsule with the assigned dose will be provided for participant self-administration using the Mighty Medic in accordance with the manufacturers operating instructions. When the Mighty Medic is activated, the dosing capsule is heated, vaporizing the substances placed inside it.

At each session, study personnel will first purge residual ethanol in the Mighty Medic in an unheated state. Detailed instructions for use of the device are available here: <https://www.storz-bickel.com/media/wysiwyg/CRAFTY-MIGHTY/PDF/mighty-vaporizer-instructions-manual.pdf> (see annex documents) and are provided in the supplementary materials section of the IRB application.

Participants will then inhale the contents of one Mighty Medic dosing capsule. Specifically, they will be given 15 minutes to inhale the contents of the capsule *ad libitum* (i.e., at their own pace). Participants will take a minimum of 15 puffs. If a visible vapor is still observed after 15 puffs, the will continue to take puffs until they no longer exhale visible vapor (this signifies that the dosing capsule is depleted; see detailed instructional materials from Storz and Bickel). This procedure will produce THC exposure of 0, or 15mg or 30mg THC, and 1mg, 5mg, or 15mg d-limonene. Participants will be able to halt self-administration of the study drug if they experience adverse effects prior to inhaling the entire dose. Similarly, study staff may halt the drug administration procedure if untoward drug effects are observed. This is not expected at the doses under investigation, but may occur in rare circumstances. Study participants and research staff will be blinded to dose assignment. The conclusion of drug administration will be considered the “0 hour” by which remaining protocol assessments will be scheduled. To prevent issues of cross-contamination, new inhalation bags and thoroughly cleaned stainless steel wool pads will be utilized for every test session.

Post-Drug Administration Procedures.

Following the “0-hour” time point (last exhalation of study drug), participants will complete a battery of assessments that includes:

- 1) Serum specimen collection at 0min, 15 min, 60 min, 120 min, and 180 min.

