computerized Paced Serial Addition Task (PSAT): Participants are provided a string of single digit numbers on the computer and must add the total of the prior to integers presented and respond by selecting the answer using the computer mouse on the screen, primary outcome is a summed score of the number of correct trials during the task. Recent studies in our laboratory have shown that these 2 tasks are sensitive to cannabis dose effects.

b. Study duration and number of study visits required of research participants.

Ten study visits will be required (11 for those who complete the additional 10th study session). One visit for screening evaluation, and 9 (with option for 10) outpatient experimental sessions lasting approximately 7 hours each. Because there are so many experimental testing sessions in this trial, and interpretation of data is contingent on a complete data set, participants may be invited to repeat a study session should circumstances arise that result in the loss of data during a session (e.g., failure to obtain blood specimens or missing cognitive testing time points), or protocol deviation that impacts data integrity. This is not expected to occur for most participants. Because the study involves repeated collection of blood samples, participants may not repeat more than 4 testing sessions (only 3 sessions may be repeated if they also completed the 10th session), as this would result in cumulative blood collection that would exceed what is typically collected during a single routine blood donation (473mL); see Risks, section 7, below. That said, it would be very unlikely for a participant to repeat more than 1 test session.

c. Blinding, including justification for blinding or not blinding the trial, if applicable.

THC/terpenoid dose assignment will be double-blinded in this study. That is standard procedure for appropriate scientific control in studies evaluating the dose effects of psychoactive drugs.

d. Justification of why participants will not receive routine care or will have current therapy stopped.

e.

Participants in this study will be healthy volunteers. Routine care for any medical illness that may arise during participation will not be affected.

f. Justification for inclusion of a placebo or non-treatment group.

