A placebo dosing session (no THC, no terpenoid) will be included to help interpret active drug effects on pharmacodynamic outcomes. Placebo dosing provides a control for expectancy effects on subjective reports and cognitive performance as well as non-pharmacological factors such as fatigue, hunger, and learning effects on performance tasks. Placebo dosing is standard for research studies involving evaluation of acute drug effects.

g. Definition of treatment failure or participant removal criteria.

This is not a treatment study. Participants may quit participation at any time of their own volition. The study investigators will discharge study participants for failing to attend their scheduled session, failure to follow the protocol requirements, or for other reasons not known at this time.

h. Description of what happens to participants receiving therapy when study ends or if a participant's participation in the study ends prematurely.

This is not a treatment trial; there is no direct course of therapy related to the participant population being targeted. We are recruiting healthy adults with experience using cannabis and who are not seeking treatment for substance use problems. Should any report the desire for treatment they will be referred to appropriate community service centers. Premature termination of participation may result in the need to recruit additional research volunteers, but should have no impact on the study volunteer directly.

5. Inclusion/Exclusion Criteria

Participants will meet the following eligibility criteria:

Inclusion Criteria

1. Have provided written informed consent
2. Be between the ages of 18 and 55
3. Be in good general health based on a physical examination, medical history, vital signs, 12-lead ECG and screening urine and blood tests
4. Test negative for drugs of abuse other than cannabis, including breath alcohol at the screening visit and at clinic admission
5. Not be pregnant or nursing (if female). All females must have a negative serum pregnancy test at the screening visit and a negative urine pregnancy test at clinic admission.
6. Have a body mass index (BMI) in the range of 18 to 36 kg/m²
7. Blood pressure at Screening Visit does not exceed a systolic blood pressure (SBP) of 150 mmHg or a diastolic blood pressure (DBP) of 90 mmHg
8. Have no allergies to any of the ingredients used to prepare vapor (THC, d-limonene).
9. Report having experienced anxiety after consuming cannabis in the past.

Exclusion Criteria

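### The optional 15 mg d-limonene session is given a comparative purpose that its fixed last position and response-based entry cannot support, and the protocol's blinding statements differ on whether they cover it.

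*Protocol*

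**What the plan says.** **Purpose.** The abstract says the tenth condition is there to find out "whether a higher dose of d-limonene can further attenuate the anxiogenic effects of THC than what is observed at the 1mg and 5mg doses".

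**Allocation.** Section 4, Protocol Overview, puts the nine primary conditions in randomised order. Of the tenth it says: "The optional 10th condition will not be randomized and will only occur after the other nine study conditions have been completed". The principal investigator must also have judged that the participant showed an anxiogenic response to THC in the earlier sessions. Section 4b allows a session to be added: "participants may be invited to repeat a study session should circumstances arise that result in the loss of data during a session".

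**History.** Section 3 dates the safety data with the words "At the time that the amendment to this protocol adding the 15mg d-limonene dose was submitted" and refers to the first 16 randomised participants. The dose was therefore added when at least 16 people had been randomised.

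**Blinding.** The abstract lists conditions 1 to 9 under double-blind administration and introduces the optional session separately, with no blinding claim. Section 4 is broader in three places:
- Protocol Overview: "All procedures will be performed in double-blind manner using a within-subject crossover design".
- Experimental Drug Exposure, in the paragraph that names 15 mg d-limonene among the exposures: "Study participants and research staff will be blinded to dose assignment".
- Section 4c: "THC/terpenoid dose assignment will be double-blinded in this study".

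**The concern.** The contrast of 15 mg with 1 mg or 5 mg d-limonene, each with 30 mg THC, sets a condition that always comes last against conditions spread at random over positions 1 to 9. Any change in anxiety ratings over sessions, such as habituation to the setting or changing expectancy, enters that contrast in full. The outcome is a self-rating, so this is plausible. Its direction is not documented: a fall would look like extra attenuation, and a rise would conceal it.

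Entry on an observed response brings a second problem. Participants chosen because some earlier ratings were high will tend to rate lower later, whatever they inhale.

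On blinding, the session has one listed content. Staff who know the protocol would know the dose, whatever the general statements say. At stake is whether a 15 mg result could be reported as a blinded dose-response finding.

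**Working it through.** **1. Position.** The nine conditions are in random order, so each comparator has mean position (1 + 9)/2 = 5. The optional session is at position 10 if nothing is repeated. The gap is 10 − 5 = 5 positions. A repeat can push the optional session later, but section 4b does not say when repeats take place, so that case is not sized here.

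**2. Bias from drift.** The protocol gives no drift, SD or between-session correlation. Assumptions: total SD 1; linear drift of 0, 0.02 or 0.05 SD per session; correlation ρ between sessions of 0.3 to 0.7; 10 to 18 of the 20 completers taking part; no true difference between 15 mg and 5 mg; no selection effect.

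Bias = drift × gap:
- 0.02 × 5 = 0.10 SD
- 0.05 × 5 = 0.25 SD

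**3. False-positive rate.** The test is a paired t-test of 30 mg THC + 5 mg against 30 mg THC + 15 mg, one-sided 2.5%. Each session has residual SD √(1 − ρ). The comparator's position is uniform on 1 to 9. There were 40,000 simulated trials per cell, with simulation error of about 0.2 percentage points or less. With no drift the rate is 2.4 to 2.6%. With a downward drift (three values for ρ = 0.3 / 0.5 / 0.7):

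| n | 0.02 SD per session | 0.05 SD per session |
|---|---|---|
| 10 | 4.2 / 4.7 / 5.5% | 8.7 / 10.6 / 14.8% |
| 14 | 4.7 / 5.4 / 6.5% | 11.2 / 13.8 / 19.8% |
| 18 | 5.4 / 6.0 / 7.2% | 13.4 / 16.8 / 24.7% |

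An upward drift of the same size would mask 0.10 or 0.25 SD of true attenuation.

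**4. Could a session-number term repair it?** Positions 1 to 9 have a sum of squares about their mean of 60. Over 20 participants that is 20 × 60 = 1,200. Removing condition means leaves about 1,200 × 19/20 = 1,140. The standard error of the slope is 1/√1,140 = 0.0296 residual SD. Carried over 5 positions, the 95% half-width is 1.96 × 5 × 0.0296 × √(1 − ρ):
- ρ = 0.3: 0.24 SD
- ρ = 0.5: 0.21 SD
- ρ = 0.7: 0.16 SD

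This is about as large as the bias to be removed. It also assumes that the trend from sessions 1 to 9 continues past session 9, which nothing in the design can check. No late repeat of 30 mg THC + 1 mg or + 5 mg is planned as a reference.

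**5. Selection.** As an illustration, suppose entry required an above-average rating in one earlier session. The expected drop from that session to a later one, with no treatment difference and no drift, is (1 − ρ) × √(2/π) = (1 − ρ) × 0.798. This gives 0.56, 0.40 and 0.24 SD for ρ = 0.3, 0.5 and 0.7. It applies only to contrasts with a session used to select. The protocol does not say which sessions enter the judgement.

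**6. Blinding, side by side.** The abstract's list stops at condition 9. The three statements in section 4 have no such limit, and one stands in the paragraph that names 15 mg. For the optional session these differ in scope. With a single listed content, the broader statements cannot hold for staff who know the protocol.

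**The case against.** The strongest defence is that the protocol is open about the design. It calls the session optional, separates it from the primary conditions, discloses that it is neither randomised nor open to all completers, and builds neither its objective nor its sample size on it. Because entry depends on an observed response, the session could not have been randomised among the nine as designed, and the amendment explains why it came late. Labels and model terms are commonly left to an analysis plan, which is not shown here. All of this stands. But purpose, allocation and blinding are fixed in the protocol itself, and no analysis can separate a dose from a position it always occupies without an assumption about the trend.

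The sizes are also hypothetical. The 25% figure needs the larger drift, the highest correlation and 18 participants. The protocol's own effect sizes, 0.87 to 1.0, are not specific to this contrast. If they are on the same scale, 0.25 SD is 25 to 29% of them (0.25/1.0 and 0.25/0.87), so an effect that large would not be erased.

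Several stronger readings are tempting but not supported:
- *No order trend can be estimated.* It can, from the randomised sessions 1 to 9. Only its extension past session 9 is untestable.
- *A placebo beside the optional session is the missing control.* Section 4f does say "Placebo dosing provides a control for expectancy effects on subjective reports", but placebo is not the comparator here. The missing reference is a late repeat of 30 mg THC with 1 mg or 5 mg.
- *Every blinding statement covers the optional session, or participants are unblinded.* The abstract limits its statement to nine conditions, and what participants are told is not visible.

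**Conclusion.** The point holds and is minor. The stated purpose goes beyond what a non-randomised, always-last session in selected completers can show, and the blinding statements are inconsistent about that session. Under the assumed drift of 0.02 to 0.05 SD per session, the bias is 0.10 to 0.25 SD and the nominal 2.5% error becomes about 4 to 7% and 9 to 25% respectively. With no drift it stays at 2.5%. Neither the size nor the direction of any drift is known from the protocol, and these rates leave out selection.

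A reader might infer that the trial's main result is compromised. It is not: the nine randomised sessions carry the primary comparison, and the optional session does not alter it. Nor do the documents show that a 15 mg result would be wrong. They show only that order, selection and dose could not be told apart. The session remains useful as description.

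**What to change.** (a) In the abstract and in section 4, Protocol Overview, replace the determine-whether purpose. State that the optional session is exploratory and outside the randomised comparison. State also that any contrast with 1 mg or 5 mg is descriptive, confounded with session order and with selection on observed response, and not evidence of further attenuation on its own. If a session-number correction is reported, say that it extrapolates a trend from sessions 1 to 9.

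(b) Reconcile the blinding statements in section 4 (Protocol Overview, Experimental Drug Exposure and 4c) with the abstract. Either limit them to the nine randomised sessions, or state what stays blind in the optional session and from whom.

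The cost is wording in the abstract and these parts of section 4, with no extra sessions or participants. The downside is that the 15 mg result can be reported only as descriptive.
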